4. STATISTICAL METHODS

4.1. Sample Size and Study Precision

The three year enrollment period of the registry is estimated to result in an enrollment of 3000 to 5000 BDQ-treated patients.

A cohort of 3000 patients gives a 95% probability of identifying an adverse event with an incidence rate of 1:1000.

Based on the sample size estimates below, a registry of 1000 BDQ-exposed patients would have 95% power to detect a Relative Risk of 2 assuming $\alpha = 0.05$ and a 1:1 ratio of BDQ-exposed patients to unexposed patients for events that occur with a frequency of at least 3%.

Power and Sample Size for Adverse Events Occurring with a Frequency of at Least 3%							
Exposed	Relative Risk						
	1.5	2	3	4	5	7	10
0	0.049985	0.049985	0.049985	0.049985	0.049985	0.049985	0.049985
100	0.133214	0.252768	0.559428	0.828643	0.961157	0.999754	1.000000
200	0.190756	0.414883	0.844041	0.986772	0.999721	1.000000	1.000000
300	0.243884	0.552078	0.952777	0.999299	0.999999	1.000000	1.000000
400	0.294233	0.663681	0.987120	0.999970	1.000000	1.000000	1.000000
500	0.342210	0.751574	0.996745	0.999999	1.000000	1.000000	1.000000
600	0.387925	0.819043	0.999224	1.000000	1.000000	1.000000	1.000000
700	0.431400	0.869774	0.999824	1.000000	1.000000	1.000000	1.000000
800	0.472639	0.907271	0.999961	1.000000	1.000000	1.000000	1.000000
900	0.511649	0.934588	0.999992	1.000000	1.000000	1.000000	1.000000
1,000	0.548449	0.954244	0.999998	1.000000	1.000000	1.000000	1.000000

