4.4.2.2. Analysis of Adverse Events

Incidence rates of adverse events will be calculated for the BDQ and non-BDQ treated cohorts. Additional descriptive analyses will include incidence rates of adverse events of interest for BDQ treated patients and non-BDQ treated patients calculated by dividing the total number of each adverse event by the total person-exposure time and expressed as the number of events per person-year, and 95% confidence intervals.

Relative risk rates and 95% confidence intervals will be calculated and appropriate stratified analyses will be conducted for each adverse event, including death. Poisson regression models will be used to adjust for potential confounders based on baseline clinical characteristics and patient demographics. Adjustments for imbalances between the treatment groups will be applied using accepted methods based on sample size availability and the observed overlap of key patient characteristics. If the sample size is adequate, propensity score methods may be used to adjust for imbalances between the 2 treatment groups before receiving the BDQ treatment or other MDR-TB therapy. Adjustment methods will be determined *a priori* to any comparative analysis with respect to safety outcomes.

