4.5. Evaluation of Appropriateness of Comparison Study

The evaluation of appropriateness of a comparison of BDQ-exposed patients with non-BDQ-treated MDR-TB patients will be based on the consistency of the clinical

experience of the 2 cohorts. This assessment will be conducted based on distribution of propensity scores for receipt of BDQ or other treatment regimens.

The evaluation of clinical experience will assess the patients' clinical and demographic characteristics in relation to receipt of BDQ and other MDR-TB regimens. Information will be captured on the patients' clinical and demographic characteristics that could be predictive of treatment appropriateness. This information will be incorporated into multivariate model to identify a group of patients with similar characteristics to the BDQ cohort but treated with other MDR-TB treatments. All patients will be assigned a propensity score ranging from 0 to 1 that represents the fitted probability of receiving BDQ. The scores from non-BDQ-treated patients will be plotted against those for BDQ-treated patients. Overlap in the cohorts based on sample size estimates of approximately 750 patients per treatment group in the propensity space must exist for a comparison of safety events between the two groups. An epidemiologist trained in propensity score estimation and matching methodology will make this assessment on the epidemiological validity of a comparison between the 2 treatment cohorts.

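### The 95% power stated for a relative risk of 2 with 1000 BDQ patients rests on an undisclosed one-sided test; with the planned 95% confidence intervals it is about 90%

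*Protocol*

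**What the plan says.** Protocol section 4.1 states that "a registry of 1000 BDQ-exposed patients would have 95% power to detect a Relative Risk of 2 assuming" an alpha of 0.05 and "a 1:1 ratio of BDQ-exposed patients to unexposed patients", "for events that occur with a frequency of at least 3"%. A table gives power for 0 to 1000 exposed patients in steps of 100, at relative risks from 1.5 to 10. The cell for 1000 patients and a relative risk of 2 is 0.954244. Neither the text nor the table says whether alpha is one-sided or two-sided, or which test is assumed.

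On the analysis, section 4.4.2.2 says: "Relative risk rates and 95% confidence intervals will be calculated and appropriate stratified analyses will be conducted for each adverse event, including death". It adds: "Poisson regression models will be used to adjust for potential confounders based on baseline clinical characteristics and patient demographics". Propensity score methods are optional there. No one-sided test and no matched-pair test is named.

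Section 4.5 sets a condition for the comparison: overlap of "approximately 750 patients per treatment group in the propensity space must exist for a comparison of safety events between the two groups". It refers to sample size estimates but states no power for that size.

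**The concern.** A reader who sees alpha of 0.05 next to planned 95% confidence intervals will take the 95% power as two-sided. The table suggests otherwise. Its zero-patient row is 0.049985 in every column, which is the tail area beyond 1.645; a two-sided 5% test would put 0.0250 in that tail.

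The relative risk of adverse events and mortality is a primary objective (section 1.3.1), and section 4.1 holds the only power statement for it. If the table is one-sided and the inference two-sided, the protocol promises more than the planned analysis delivers. For a 3% event at 1000 per group, the chance of missing a doubling would be about 10%, not about 5%.

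**Working it through.** **Inputs.** From section 4.1: unexposed frequency p0 = 0.03, relative risk RR, exposed frequency p1 = 0.03 × RR, 1:1 allocation, alpha 0.05. From section 4.4.2.2: 95% confidence intervals, taken as two-sided, so the critical value is 1.96. From section 4.5: 750 per group. Reading 3% as the unexposed frequency is an interpretation, which step 1 confirms.

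**Step 1. Reproduce the printed table.** For n pairs with independent members, let d = p1 − p0 and ψ = p1(1 − p0) + p0(1 − p1). Then

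power = Φ{[d√n − z√ψ] / √(ψ − d²/ψ)}.

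At RR 2: d = 0.03, ψ = 0.06 × 0.97 + 0.03 × 0.94 = 0.0864, and √(ψ − d²/ψ) = 0.27565. With z = 1.645 and n = 1000:

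(0.03 × 31.623 − 1.645 × 0.29394) / 0.27565 = 1.6875, and Φ(1.6875) = 0.954244.

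This equals the printed cell. Others agree as well:

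| n | RR | Formula | Printed |
|---|---|---|---|
| 100 | 2 | 0.252768 | 0.252768 |
| 700 | 2 | 0.869774 | 0.869774 |
| 100 | 3 | 0.559428 | 0.559428 |
| 1000 | 1.5 | 0.548449 | 0.548449 |

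All 70 cells from n = 100 to n = 1000 agree to within 6 × 10⁻⁷. The unmatched formulas tried (pooled and unpooled proportions, log relative risk, Poisson log rate, arcsine), one-sided or two-sided, do not match cell for cell.

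The zero-patient row does not follow this formula, which would give 0.0397 at RR 2 and n = 0. Its constant value is Φ(−1.645) = 0.049985, which independently points to the same critical value.

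**Step 2. Same formula, two-sided.** With z = 1.96 and n = 1000: (0.94868 − 0.57612) / 0.27565 = 1.3516, power 0.912.

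**Step 3. Unmatched comparison of two proportions, two-sided.** The mean frequency is 0.045. At n = 1000 the standard error is √(2 × 0.045 × 0.955 / 1000) = 0.009271 under the null and √[(0.03 × 0.97 + 0.06 × 0.94) / 1000] = 0.009247 under the alternative. Then (0.03 − 1.96 × 0.009271) / 0.009247 = 1.279, power 0.900.

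A Poisson log-rate approximation, closest in form to the planned model, has standard error √(1/60 + 1/30) = 0.2236. Then 0.6931/0.2236 − 1.96 = 1.140, power 0.873. In simulation, unadjusted two-sided tests and intervals (score, log relative risk and Poisson) rejected in 89.6% to 90.7% of runs, so about 90% is a fair summary.

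**Step 4. Results side by side (p0 = 0.03).**

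| Case | 4.1 basis (one-sided, matched) | Two-sided, matched | Two-sided, unmatched |
|---|---|---|---|
| RR 2, 1000 per group | 95.4% | 91.2% | 90.0% |
| RR 2, 750 per group | 89.0% | 81.3% | 80.1% |
| RR 1.5, 1000 per group | 54.8% | 42.1% | 42.3% |

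Two-sided power of 95% at RR 2 needs 1178 pairs (about 1180) or 1239 per group unmatched (about 1240).

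**Step 5. Where the drop comes from.** One-sided unmatched power at 1000 per group is 94.5%. Of the 5.4 points between 95.4% and 90.0%, sidedness accounts for 4.2 (95.4 to 91.2) or 4.5 (94.5 to 90.0), depending on the order of the steps. The matched-pair formula accounts for about one point.

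**Step 6. The 750 in section 4.5.** Two-sided unmatched power of 80% at 3% versus 6% needs 749 per group. That fits 750 closely, whereas the 4.1 formula gives 89.0% there.

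**The case against.** The stated 95% agrees with its own table, so there is no slip of arithmetic. Sidedness is unstated rather than expressly contradicted, and a one-sided test for harm can be defended. Both points are fair. But the protocol declares no one-sided test and plans 95% confidence intervals, so the stated power does not belong to the stated inference.

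A matched analysis is not ruled out: section 4.5 mentions matching methodology, and section 4.4.2.2 leaves propensity methods open. This stands, but matters little. A matched analysis reported with a 95% interval has 91.2% power, still not 95%.

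Section 4.1 expects 3000 to 5000 BDQ patients, so 1000 may be only illustrative. With that many and enough comparators, power would exceed these figures. Comparator numbers are not fixed, however, and the 1000-patient sentence is the one the protocol offers.

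Some stronger readings are tempting but unsupported:

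- A reader might infer that the mortality comparison is underpowered. Section 1.1.5 gives mortality of 8% to 21% in good programmes, and 11% and 15% in meta-analyses. At 8%, 11% and 15%, two-sided unmatched power for a relative risk of 2 at 750 per group is 99.8%, over 99.9% and over 99.9%. The shortfall concerns events near 3%.
- A reader might set the 20% miss rate at 750 against the 5% stated for 1000 and call it a fourfold error. Section 4.5 claims no power for 750, and the 4.1 formula already implies an 11% miss rate there.
- A reader might conclude that 750 is wrong, or should give way to a power threshold that admits unbalanced cohorts. It matches a conventional 80% two-sided target, and it also governs propensity overlap, judged for epidemiological validity. Replacing it would be a design preference.

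**Conclusion.** The point holds. The 95% power in section 4.1 is a one-sided figure from a matched-pair formula, and neither feature is disclosed. Under the planned 95% confidence intervals, power for a relative risk of 2 at 1000 per group is about 90%. Sections 4.1 and 4.5 appear to rest on different bases, although the protocol does not say how 750 was derived.

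This assumes that the 95% intervals are two-sided, an unexposed frequency of exactly 3% (the least frequent event the claim covers), equal groups and no confounder adjustment. Adjustment would generally lower power further; more frequent events or larger cohorts would raise it. The one-sided reading of the table is an inference, but an exact reproduction of the printed cells supports it. What needs correcting is the stated power, not the recruitment target.

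**What to change.** In section 4.1, state the sidedness and the test, and recompute the table with two-sided alpha 0.05 and a method that matches the planned analysis. Restate the claim as about 90% power for a relative risk of 2 with 1000 per group at a 3% unexposed event frequency; if 95% is still wanted as a benchmark, give about 1240 per group. In section 4.5, keep the 750 and add that it corresponds to about 80% two-sided power for a relative risk of 2 at a 3% event frequency.

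The cost is one recalculated table and a few sentences. No extra patients are needed. The drawback is that the stated power looks less favourable.

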4.2. Measurements

Janssen is currently collaborating with the WHO to outline a comprehensive list of data elements and definitions as well as data collection instruments.

4.2.1. Exposure Definition and Measures

Exposure to MDR-TB regimens will be determined by documentation by the healthcare provider. The initiation date of MDR-TB treatment for each patient will be the drug initiation date as reported by the healthcare provider. The discontinuation date for each drug exposure will be defined as the date the drug was stopped as reported by the healthcare provider. Duration of exposure will be based on initiation and discontinuation dates for each drug. Switches from one drug to another will be captured and time on drug will be defined by the exposure periods.

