2. OVERVIEW OF STUDY DESIGN

2.1. Study Design

The research design uses a prospective observational comparative cohort study of patients treated for MDR-TB in multiple countries included in the early adopter (WHO pilot) program. A case of tuberculosis is one in which a health worker (clinician or other medical practitioner) has diagnosed TB. MDR-TB is defined as TB caused by *Mycobacterium tuberculosis* resistant in vitro to the effects of isoniazid and rifampicin, with or without resistance to any other drugs. Patients are enrolled in the registry by their healthcare provider once the healthcare provider diagnoses a patient with MDR-TB (inception cohort for comparison) or decides to treat with BDQ (exposure cohort specifically identifying indication for use for BDQ). All patient follow-up data will be collected at each visit from the healthcare provider during the course of BDQ treatment and for an additional 24 months after the last BDQ dose unless the patient is lost to follow-up or has died. Similar follow-up will be conducted for MDR-TB patients not treated with BDQ. Two options are under evaluation for the recruitment of MDR-TB patients not treated with BDQ. The first option under consideration is to include patients who are eligible for BDQ, but refuse BDQ at sites where BDQ is available. The second

option under consideration is the use of a stepwise cluster wedge design to enroll patients at centers who would be eligible for BDQ, but do not have access. The method for selecting MDR-TB patients not treated with BDQ will depend on how BDQ is made available in the early adopter countries. All patients newly diagnosed and treated for MDR-TB will be eligible for inclusion in the registry. Additionally, all patients initiating BDQ treatment will be eligible for inclusion in the registry regardless of the indication for use. All patients meeting the inclusion criteria and providing informed consent for participation in the study will be enrolled. The registry enrollment period will be open for 36 months with an additional 24 months of follow-up for safety assessment. This enrollment period should allow the enrollment of approximately 3000 MDR-TB patients treated with BDQ.

Data will be collected in an observational manner such that the management of the patient is determined by the patient and the caregiver and not influenced by the registry protocol. The registry will describe care as it is provided.

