3.1.3. Data Source(s)

3.1.3.1. Healthcare Providers

Data for the registry will be gathered by healthcare providers treating patients MDR-TB at participating centers that evaluate, diagnose and treat patients with MDR-TB. Data will be recorded at patient enrollment and at each subsequent patient visit.

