6.2. Informed Consent

Each subject must give written consent according to local requirements after the nature of this research study has been fully explained. The informed consent form (ICF) must be signed before any study-related data is collected. The ICF used must be approved by the reviewing IRB and acceptable to JRD. The ICF should be in accordance with principles that originated in the Declaration of Helsinki, current ICH and GCP guidelines, applicable regulatory requirements, and JRD policy. The collection and processing of personal data from subjects enrolled in this study will be limited to data necessary to fulfill the objectives of the study. Sample data and corresponding relevant clinical data will be made non-identifiable by the removal of personal identifiers.

A subject may withdraw their consent for this research study through the contact information given on the Informed Consent. JRD will not use the collected data upon receipt of such a request. However, data that have already been processed will be retained by JRD to avoid compromising data analysis.

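### Exposure time starts at the reported first dose with no rule for on-drug time before enrollment, so any such gap adds guaranteed-survival time to the death rates

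*Protocol*

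**What the plan says.** Protocol section 4.2.1 sets the start of treatment: "The initiation date of MDR-TB treatment for each patient will be the drug initiation date as reported by the healthcare provider". It then sets the length: "Duration of exposure will be based on initiation and discontinuation dates for each drug". Section 4.4.2.2 gives the rate for adverse events of interest as "dividing the total number of each adverse event by the total person-exposure time", and its next paragraph treats death as one of the events for which a relative risk is calculated.

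On entry to the registry, section 2.1 enrolls patients "once the healthcare provider diagnoses a patient with MDR-TB (inception cohort for comparison) or decides to treat with BDQ". The inclusion criteria in section 3.1.1 are looser. They take in patients newly diagnosed with MDR-TB and patients newly treated with BDQ, with no limit on the time since first dose. Section 6.2 says of the consent form: "The informed consent form (ICF) must be signed before any study-related data is collected". Section 3.1.3.1 adds: "Data will be recorded at patient enrollment and at each subsequent patient visit".

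No section starts person-time at enrollment or says how on-drug time before enrollment is to be handled.

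**The concern.** A patient can be counted as a death in the registry only if he or she was alive to consent. If first dose comes before consent, the interval between them is time in which no counted death is possible, yet under sections 4.2.1 and 4.4.2.2 as written it belongs to the exposure time. The numerator covers time after enrollment and the denominator covers time after first dose. For non-fatal events the mismatch is weaker, because they can be recorded later, but the protocol requires no systematic look-back.

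Two routes to a gap are open:

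- Section 3.1.1 does not require consent before the first dose.
- A patient enrolled at the BDQ decision may already be on an MDR-TB regimen. Section 4.2.1 dates MDR-TB treatment as well as each drug, and section 4.4.2.2 does not say whether exposure means BDQ time or regimen time. If it means regimen time, the earlier months count. If it means BDQ time, they do not.

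Section 1.3.1 makes the relative risk of adverse events and death, BDQ against no BDQ, a primary objective. A gap that is longer in one cohort moves that ratio. Section 2.1 leaves the method of recruiting comparators open, so nothing in the protocol makes the gap equal in the two cohorts.

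**Working it through.** The protocol states no figure on this point, so there is none to reproduce. The calculation below shows only how the bias scales.

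**Inputs**

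- T, exposure time per patient: 24 months. Section 1.1.4 speaks of up to 2 years of treatment. T of 6 and 12 months are added as assumptions.
- g, gap from first dose to enrollment: assumed, since the protocol gives no value.
- Constant hazard, and no event in the gap counted. For deaths the second condition holds by construction. For non-fatal events it is the worst case.

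**Rate in one cohort.** Calculated rate / true rate = (T − g) / T.

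| T (months) | g = 0 | g = 0.5 | g = 1 | g = 3 | g = 6 |
|---|---|---|---|---|---|
| 24 | 1.00 | 23.5/24 = 0.979 | 23/24 = 0.958 | 21/24 = 0.875 | 18/24 = 0.75 |
| 12 | 1.00 | 0.958 | 0.917 | 0.75 | 0.50 |
| 6 | 1.00 | 0.917 | 0.833 | 0.50 | – |

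At T = 24, gaps of 0.5, 1 and 3 months lower the rate by 2.1%, 4.2% and 12.5%.

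**Rate ratio.** With gaps gB (BDQ) and gC (comparison) and the same T, the true ratio is multiplied by (T − gB) / (T − gC). At T = 24:

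| gB | gC | Factor | A true ratio of 2 reads as |
|---|---|---|---|
| 1 | 1 | 23/23 = 1.00 | 2.00 |
| 1 | 0 | 23/24 = 0.958 | 1.92 |
| 3 | 0 | 21/24 = 0.875 | 1.75 |
| 6 | 0 | 18/24 = 0.75 | 1.50 |
| 0 | 1 | 24/23 = 1.043 | 2.09 |
| 0 | 3 | 24/21 = 1.143 | 2.29 |

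A gap mainly in the BDQ cohort hides excess risk. A gap mainly in the comparison cohort creates or inflates it.

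**Effect of delayed entry.** Counting time from the later of first dose and enrollment gives, per unit hazard, (T − g) / (T − g) = 1.00 under a constant hazard, and changes nothing when g = 0.

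If the hazard in the first 3 months is three times the later one (assumed), with T = 24 and g = 1:

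- True mean hazard, in units of the later hazard: (3×3 + 21)/24 = 1.25.
- Uncorrected: (3×2 + 21)/24 = 1.125, and 1.125/1.25 = 0.90.
- Delayed entry: 27/23 = 1.174, and 1.174/1.25 = 0.94.

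Delayed entry then makes numerator and denominator match, but it does not recover the unobserved early risk.

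**The case against.** The strongest answer is the enrollment trigger. Diagnosis and the decision to give BDQ both nominally precede the first dose of the index treatment, and section 2.1 calls the comparison group an inception cohort. Under that design the gap, and with it the bias, is zero. This stands as the usual case. It does not close the point, because the inclusion criteria do not enforce the trigger and because a patient can be on a regimen before BDQ is decided.

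A reader might infer from section 6.2 that all time before consent is event-free. The documents do not support that. The consent rule governs when data may be collected, not the dates of the events. Section 4.2.2 records adverse events over the course of therapy, section 4.2.2.1 counts treatment-emergent events from the first BDQ dose, and section 4.6 lets medical records be transcribed to the case report form. Non-fatal events in the gap can therefore be captured, if perhaps incompletely. Only for deaths is the gap empty by construction.

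A reader might also infer a large distortion of the ratio. With 18 months of exposure and lags of 0.5 month (BDQ) and 6 months (comparison), a true ratio of 1 would read 17.5/12 = 1.46. Both lags and the 18 months are assumptions, and a 6-month comparator lag sits badly with an inception cohort.

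Finally, the separate statistical analysis plan is not shown and may settle the matter. That is fair as to detail. But the protocol itself fixes the start date, the stop date and the rate formula, and followed literally they include the gap.

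**Conclusion.** The point holds as a gap in the protocol's rules, not as a demonstrated bias. For any patient enrolled after the first dose, the stated definitions put guaranteed-survival time into the death-rate denominator. Non-fatal events in that time may be under-ascertained. The death rate is then too low, and the rate ratio is wrong if the gap differs between cohorts.

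The size depends entirely on lags that the protocol does not give. With 24 months of exposure and a constant hazard, it is about 2% to 4% for a gap of up to a month and 12.5% for three months. Shorter exposure makes it larger: a 1-month gap in 6 months of exposure is 17%. Equal gaps with equal exposure leave the ratio unchanged, and a zero gap leaves everything unchanged. The matter deserves correction because it touches a primary objective and the correction is cheap.

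**What to change.** In sections 4.2.1 and 4.4.2.2, state that for the comparative death and adverse event rates both person-time and events count from the later of first dose and enrollment, in both cohorts, and say whether exposure means BDQ time or regimen time. Keep the full drug dates for describing utilization. Describe adverse events between first dose and enrollment separately, under the treatment-emergent definition in section 4.2.2.1, so that recorded early events are not lost. Report the distribution of the lag from first dose to enrollment by cohort.

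The cost is a sentence or two and minor programming with the drug start and enrollment dates. There are three downsides: slightly less person-time, early recorded adverse events leave the comparative rates, and early risk that was never observed is not recovered if the hazard is higher soon after the start.
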